#### 8.4.6 Eye examination

Dilated fundoscopy or fundus photography should be performed by the investigator, a local ophthalmologist or an optometrist according to local practice at the visits specified in Section  $\underline{2}$ . Result of the dilated fundoscopy/ fundus photography will be interpreted locally by the investigator in relation to the trial. The evaluation must be documented, signed and dated.

The evaluation must follow the categories:

- Normal
- Abnormal
  - Was the result clinically significant? (Yes/No)

Any abnormal, clinical significant findings at randomisation visit (Visit 3) must be recorded as concomitant illness.

Any clinical significant worsening from Visit 3 must be recorded as an AE (see Section 12.1)

If an eye examination has been performed within 90 days prior to Visit 3 as part of routine practice, and if the results are available prior to randomisation (Visit 3), the procedure does not have to be repeated, provided no worsening of visual function has occurred in the meantime. The investigator must still interpret, sign and date the fundoscopy/ fundus photography results. If the fundoscopy/ fundus photography is performed before the subject has signed the informed consent form, it must be documented in the subjects medical records that the reason for performing the procedure was not related to this trial. At Visit 63 the fundoscopy/ fundus photography may be performed in a time window of 2 weeks prior and 2 weeks after the visit and at Visit 89 the fundoscopy/ fundus photography may be performed 2 weeks prior to the visit.

#### 8.4.7 Physical examination

Physical examination will be performed at selected visits according to Section  $\underline{2}$ . The examination will include:

**CONFIDENTIAL** 

Date: Version: Status: Page: 07 May 2015 2.0 Final 68 of 141

- General appearance
- Head, ears, eyes, nose, throat, neck
- Respiratory system
- Cardiovascular system
- Gastrointestinal system incl. mouth
- Musculoskeletal system
- Central and peripheral nervous system
- Skin
- Lymph node palpation
- Thyroid gland

Any abnormal, clinically significant findings at screening visit (Visit 1) must be recorded as concomitant illness.

Any clinically significant worsening from Visit 1 must be reported as an AE (see Section 12).

#### 8.4.8 Vital signs

The following vital signs will be assessed at selected visits according to Section 2:

- Systolic and diastolic blood pressure (mmHg). Subjects should rest in a sitting position for 5 minutes
- Pulse. Subjects should rest in a sitting position for 5 minutes
- Body temperature, ear
- Respiratory rate (breath/minutes)
- Overall interpretation of vital signs

Any abnormal, clinically significant findings at screening visit (Visit 1) must be recorded as concomitant illness.

Any clinically significant worsening from Visit 1 must be reported as an AE (see Section 12.1).

#### 8.5 Laboratory assessments

The timing of the blood samples are outlined in the flow chart (see Section  $\underline{2}$ ). Laboratory assessments can be done at another day than on the day of the actual visit as long as it is within the visit window.

Review of laboratory reports must be documented either on the document and/or in the subject's medical record.

The laboratory equipment may provide analyses not requested in the protocol but produced automatically in connection with the requested analyses according to specifications in the laboratory

Protocol Trial ID: NN9828-4150 UTN: U1111-1154-7172 EudraCT no.: 2014-001215-39	07 May 2015 on: 2.0 s: Final 69 of 141	Novo Nordisk
--	---	--------------

standard operating procedures. Such data will not be transferred to the trial database, but abnormal values will be reported to the investigator. The investigator must review all laboratory results for concomitant illnesses and AEs and report these according to this protocol.

In the case of an 'abnormal, clinically significant' finding, the investigator must comment in the subject notes and, if it occurs at screening visit (Visit 1), record this on the concomitant illness/medical history form.

Any clinically significant worsening after Visit 1 must be reported as an AE (see Section 12.1).

All blood samples will be sent to the central laboratory. Instructions for obtaining samples, handling conditions including coding in order to keep subject identity confidential, storage, blood sampling, storage and shipping will be described in a trial specific laboratory manual supplied by the central laboratory. Some samples will be shipped to the central laboratory, from where they will be shipped to specialised laboratories for analysis. It will be specified below if samples are analysed at site or at a specialised laboratory, all other samples will be analysed at the central laboratory.

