#### 8.1.5 Investigator's assessment

It is the responsibility of the investigator or delegated staff to review the e-diaries, PROs, ECGs, eye examinations (fundoscopy/ fundus photography), laboratory reports etc. This must be documented with the investigator or delegated staff's dated signature either on the front page of the documents and/or in the subject's medical records. The signed documents must be retained at the investigator site as source documentation.

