#### Immunology

T1DM is mediated by immune destruction of the islets, characterised by T-cell infiltrate and detectable autoantibodies in the periphery. Additionally, IL-21 is an important immune-modifying cytokine that has been demonstrated to impact B- and T-cell compartments. The assays proposed will assess the disease- and treatment-associated effects on the immune response mediating T1D.

Samples will be drawn according to Section  $\underline{2}$ . The investigator must record the date and the exact time for sampling the blood.
Protocol		Date:	07 May 2015	Novo Nordisk
Trial ID: NN9828-4150	CONEIDENTIAL	Version:	2.0	
UTN: U1111-1154-7172	CONFIDENTIAL	Status:	Final	
EudraCT no.: 2014-001215-39		Page:	71 of 141	

The following will be analysed:

- T-cell profiling including islet-specific auto reactive CD8+ T-cells
- IL-21, excepted at Visit 2

The blood sampling for assessment of T-cell profiling including islet-specific auto reactive CD8+ T-cells should preferably be performed at about the same time of day for a given subject.

Blood sampling for the assessment of II-21 should be taken pre-dose of the NNC0114-0006 administration. IL-21 will be analysed at a specialised laboratory only if a functioning assay is available in due time to ensure analyses and results are ready for data base lock. The investigator will receive the results of the immunology assessments at the end of the trial. If no functional assay is available the samples will be destroyed.

The periphery blood mononuclear cells (PBMCs) used for the analyses of the T-cell profiling including islet-specific auto reactive CD8+ T-cells will be stored for up to 15 years for potential future assessments if the subject has consented to it (see Section 24.2).

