# 8.5.2.2 Anti-drug antibodies

Assessment of antibodies against liraglutide and NNC0114-0006 (anti-drug antibodies) in serum will be performed at specialised laboratories according to Section  $\underline{2}$ .

Protocol Trial ID: NN9828-4150 UTN: U1111-1154-7172 EudraCT no.: 2014-001215-39	Date:07 May 2015Version:2.0Status:FinalPage:72 of 141	Novo Nordisk
--	---	--------------

Samples for the determination of anti-drug antibodies must be drawn in a fasting state to minimise interference of endogenous GLP-1. During the treatment period samples must be drawn prior to administrating trial products.

The investigators will not receive the results until the trial is completed and unblinded. A detailed description of the assay methods will be included in the antibody analysis report at the end of the study.

Antibody samples may be retained until drug approval by FDA and/or EMA. The retained antibody samples may be used for further characterisation for antibody responses towards drug if required by health authorities or for safety reasons. At end of trial the specialised laboratories responsible for the anti-drug antibodies analysis will arrange the transfer of samples to Novo Nordisk for storage. Anti-drug antibodies are stable for many years when stored frozen (e.g. -20 degrees Celsius), and further characterisation is therefore possible. Samples will only be used for further characterisation if required by the authorities (FDA and/or EMA) or for safety reasons.

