#### 8.5.2.7 Cytokines

The following will be analysed according to Section  $\underline{2}$ :

• Cytokine panel (IL-6, IL-10, IL-17, IFN $\gamma$ , TNF- $\alpha$ )

The investigators will not receive the results until the trial is completed.

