#### 8.5.3.3 Serum concentration of NNC0114-0006 for pharmacokinetics

PK samples will be taken according to Section  $\underline{2}$ . At Visit 3 and 55, samples will be taken pre-dose (up to 60 min before) and 1 hour after start of the infusion. At NNC0114-0006 dosing visits, the sample should be taken pre-dose. The investigator must record the date and the exact time for sampling the blood.

Serum will be analysed by use of an enzyme-linked immunosorbent assay (ELISA) specific for NNC0114-0006. The ELISA is validated for human serum samples.

All samples from subjects receiving active treatment with NNC0114-0006 will be analysed for NNC0114-0006. For subjects receiving placebo or liraglutide treatment only, the samples taken 1 hour after the start of infusion at Visit 3 will be analysed in order to verify the placebo treatment. If the NNC0114-0006 concentration in this sample is above the lower limit of quantification (LLOQ), all samples from that subject will also be analysed. A copy of the subject treatment allocation report will be forwarded to the laboratory before any analyses are started.

The analysis will be performed by a specialised laboratory. Investigators will not receive the results until the trial is completed and unblinded.

The PK samples will be retained until the clinical trial report (CTR) has been finalised. The samples will be stored at the specialised laboratory.

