#### 13.2 Case report form flow

The investigator must ensure that data is recorded in the eCRF as soon as possible, preferably within 5 days after the visit. Once data has been entered, it will be available to Novo Nordisk for data verification and validation purposes. Queries will be generate in the eCRF on an ongoing basis, and the investigator should solve these queries preferable **within 3 business days**.

At the end of the trial the investigator must ensure that all remaining data have been entered into the eCRF **no later than 24 hours** after the last visit at the trial site to ensure the planned lock of the database. In addition queries must be solved immediately in order to ensure the planned lock of the database.

Site specific eCRF data (in an electronic readable format) will be provided to the trial site before access to the eCRF is revoked. This data must be retained at the trial site.

When access to update the AE form in the eCRF application is removed, the investigator must record any AE follow-up information, if required, on the paper CRFs provided.

Laboratory reports will be retained at the sites.

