#### 2.9 Section 5.3.3 Insulin treatment

During the trial subjects will receive insulin treatment in order to achieve metabolic control according to the insulin titration guideline (Appendix A). This insulin treatment will be handled by the local trial sites in collaboration with Novo Nordisk's Insulin Titration Group. *Bolus and/or basal insulin can be stopped or paused at all times during the trial at the discretion of the investigator. The subject's need for bolus insulin will be documented in the eCRF.* It is acceptable to pause or stop insulin treatment if the investigator assesses that the subject is in remission.

**Insulin reduction on the day of liraglutide/ liraglutide placebo initiation and escalation** As it is a blinded trial, wWhen liraglutide/ liraglutide placebo is initiated, the total daily prerandomisation insulin dose should be reduced by 25 % for a minimum of 24 hours after the initiation of liraglutide/ liraglutide placebo.

Thereafter the insulin dose should be adjusted according to the glucose target in Table 5-2. *As it is a blinded trial this insulin reduction applies to all treatment arms.* 

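### The protocol withholds antibody, cytokine and drug-concentration results from sites but has no such rule for post-baseline C-peptide, a modest and avoidable cue to allocation for the investigators who manage insulin

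*Protocol*

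**What the plan says.** **Default.** Protocol 8.5 requires documented review of laboratory reports and adds: "The investigator must review all laboratory results for concomitant illnesses and AEs and report these according to this protocol". Section 8.1.5 repeats the duty ("It is the responsibility of the investigator or delegated staff to review the e-diaries, PROs, ECGs"), and its list goes on to name laboratory reports. Section 13.2 adds: "Laboratory reports will be retained at the sites".

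**Stated exceptions.** For anti-drug antibodies (8.5.2.2): "The investigators will not receive the results until the trial is completed and unblinded". For cytokines (8.5.2.7): "The investigators will not receive the results until the trial is completed". For NNC0114-0006 concentrations (8.5.3.3): "Investigators will not receive the results until the trial is completed and unblinded". Section 8.5.3.4 says the same for liraglutide concentrations.

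**C-peptide.** Fasting C-peptide (8.5.1.1) and the 11-point mixed meal tolerance test (MMTT) profile (8.3.1, 8.5.1.2) carry no such sentence. I found none in Amendments 1 to 7 or the SAP. Amendment 2 makes the Visit 2 peak an eligibility and stratification value, so something from Visit 2 must reach the site.

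**Who acts.** Appendix A, section 1, lets the investigator overrule the titration guideline. Amendment 2, revising 5.3.3, states: "Bolus and/or basal insulin can be stopped or paused at all times during the trial at the discretion of the investigator". SAP 2.4.1.1 derives weeks off bolus insulin from a CRF question on whether bolus has been stopped. Change in total daily insulin dose is a key supportive endpoint.

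**The concern.** Where the sponsor wanted a result kept from sites, it said so. The analyte that defines the primary endpoint, and that the sponsor expects to differ between arms, has no such protection. The flow charts give eight fasting values (weeks 6, 12, 18, 24, 30, 36, 42 and 48) and three meal tests (weeks 12, 24 and 36) before week 54.

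An investigator who sees C-peptide holding up may suspect active treatment and be readier to reduce or stop insulin; one who sees it falling may not. Part of any between-arm difference in insulin dose, number of injections or weeks off bolus insulin could then reflect guessed allocation. Week-54 and week-65 values could act in the same way on the week-80 endpoints, a period during which Amendment 7 says investigators remain blinded.

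**Working it through.** **Inputs** (Protocol 17.1, SAP 2.1): preservation at week 54 of 65% on placebo and 98% on the combination; SD of the log ratio 1 and 0.5; 60 completers per arm; two-sided 5%.

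**The plan's own figure.** d = ln(0.98/0.65) = 0.411 and SE = √[(1² + 0.5²)/60] = 0.144. A noncentral t with Satterthwaite degrees of freedom gives power 0.803, against 0.804 stated. All nine rows of the power table agree within 0.002, so the inputs are read correctly.

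**How much one C-peptide ratio reveals.** Take a subject who is equally likely to be on combination or placebo. Cut halfway between the two log medians and call a ratio above the cut combination. The proportion classified correctly is

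½[Φ(d/(2σ₀)) + Φ(d/(2σ₁))].

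At week 54 the cut is √(0.65 × 0.98) = 0.80, and accuracy is ½[Φ(0.205) + Φ(0.411)] = ½[0.581 + 0.659] = **0.620**.

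At the plan's two smaller effects, 95% and 85% preservation, the same formula gives 0.612 and 0.580. If both SDs were 0.5 (my assumption), the 98% case gives Φ(0.411) = 0.659.

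**Earlier visits.** The plan gives no week-12 to week-36 distributions. I extend its linear decline to both arms, p₀ = 1 − 0.35·t/54 and p₁ = 1 − 0.02·t/54, and hold the SDs at 1 and 0.5 (assumption).

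| Week | p₀ | p₁ | d | Accuracy |
|---|---|---|---|---|
| 12 | 0.922 | 0.996 | 0.077 | 0.5229 |
| 24 | 0.844 | 0.991 | 0.160 | 0.5478 |
| 36 | 0.767 | 0.987 | 0.252 | 0.5749 |

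Smaller SDs at early visits would sharpen the cue. Halving both (again an assumption) turns the formula into ½[Φ(d) + Φ(2d)], which gives 0.55, 0.59 and 0.65.

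The separation carried by the fasting values cannot be sized, because the documents give no planning figures for them.

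**The case against.** **Disclosure is inferred.** The sentence in 8.5 serves adverse-event detection and follows a remark on analyses produced without being requested. Sections 8.1.5 and 13.2 concern whatever reports a site receives. The laboratory manual could mask C-peptide. This stands: the documents do not support saying that sites are known to see it. They do support saying that the protocol leaves it open where it closes comparable cases.

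**Timing and number of arms.** The week-54 result comes from Visit 63, after the last liraglutide dose, so it cannot influence insulin decisions in the treatment period. Sites also face four arms, and the plan gives no effect for the two monotherapies. Both points stand. The earlier-visit figures are therefore the relevant ones for the treatment period, and the real guessing task is harder than the two-arm one worked here.

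**Other cues and safeguards.** Self-measured glucose, HbA1c, weight and gastrointestinal events (reported by 42% in the liraglutide development programme, Protocol 18.1) remain visible whatever is done about C-peptide. Titration follows self-measured glucose, reasons for deviation are documented, and a central titration group monitors the data (Protocol 14.2; Appendix A, sections 3.6 and 5). Injections and weeks off bolus insulin are only summarised descriptively. These points limit the effect. They do not remove the discretion over stopping insulin.

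**Stronger readings a reader might draw.** An optimal two-class rule would score about 68% at week 54. Most of that comes from the assumed SD difference: with equal medians and no treatment effect the same approach still scores 66%. It also has to call ratios above about 2.3 placebo, which no clinician would do. Nor can the cue be turned into a percentage-point bias in bolus stopping, because the documents give no figure for how far a guess changes behaviour. Immunology should not be counted among the withheld results either: Amendment 3 rewrote that subsection, and the withholding sentence appears to belong to the replaced text.

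**Conclusion.** The gap holds as a gap in the text. Protocol 8.5 sets review of all laboratory results as the default, and no exception covers post-baseline fasting or MMTT C-peptide. Whether sites in fact receive the values depends on a manual that is not available.

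The cue is modest: about 62% correct classification from one week-54 ratio, and about 52–57% at weeks 12–36. These figures rest on the plan's planning values, a two-arm guess, linear decline and unchanged SDs; the earlier-visit figures rise to 55–65% if the SDs are halved.

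The endpoints exposed are supportive ones: insulin dose, injections and weeks off bolus insulin. A reader might infer that the trial is unblinded or that the primary comparison is biased. The documents support neither. The primary endpoint is a central-laboratory value, reached only indirectly through insulin management or a discretionary stop of a meal test. This is a cheap improvement and does not threaten the main result.

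**What to change.** Add to Protocol 8.5.1.1 and 8.5.1.2 that post-baseline C-peptide results, fasting and MMTT, are not released to investigators until the trial is completed, as 8.5.2.7 already does for cytokines. Make the review sentence in 8.5 subject to these exceptions. At Visit 2, have the central laboratory report only what is needed: whether the peak meets the 0.2 nmol/l criterion, and the stratum relative to 0.6 nmol/l. If the laboratory manual already masks these results, the protocol should say so.

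The cost is a setting in the central-laboratory reports and a few lines of text. Sites lose C-peptide as background information. The titration guideline in Appendix A works from self-measured glucose, carbohydrate intake, insulin doses and hypoglycaemia, and the withdrawal criteria in 6.6 do not use C-peptide, so nothing either one requires is lost.

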#### 8.5.1 Laboratory assessments for efficacy

#### 8.5.1.1 Glucose metabolism

The following will be analysed:

- $HbA_{1c}$  will be measured according to Section 2, except at Visit 1.
- Fasting plasma glucose (FPG) will be measured according to Section 2, except at Visit 1. For the measurement of FPG the subject must be fasting according to Section 8.1.8.
- Fasting glucagon will be measured according to Section 2, except at Visit 1. For the measurement of fasting glucagon the subject must be fasting according to Section 8.1.8.
- Fasting C-peptide will be measured according to Section 2, except at Visit 1. For the measurement of C-peptide the subject must be fasting according to Section 8.1.8.
- PG (non-fasting) will be measured at Visit 1.
- C-peptide (non-fasting ) will be measured at Visit 1.

#### 8.5.1.2 Mixed meal tolerance test

Please refer to Section 8.3.1 for details on the samples for the 11 points C-peptide and glucose profiles.

#### 8.5.1.3 Biomarkers

#### Differentially methylated INS DNA

Minimally invasive methods to determine episodes of beta-cell death could be a valuable tool for patient stratification in clinical trials, assessing clinical response to therapy, and directing patient

Trial ID: NN9828-4150 CONFIDENTIAL Date.   UTN: U1111-1154-7172 CONFIDENTIAL Version:   EudraCT no.: 2014-001215-39 Page: Page:	2.0 Final 70 of 141	NOVO NOI UISK
---	---------------------------	---------------

care. When beta-cells die, they release insulin (INS) DNA that can be measured in serum. Though the INS gene can be detected in cells other than beta-cells, the methylation status of this gene is tissue-dependent, e.g., beta-cell-derived INS is hypomethylated. The differentially methylated INS DNA assay is hypothesized to identify waves of beta-cell death by measuring the ratio of methylated to unmethylated insulin DNA, thus providing a method of assessing beta-cell loss.

Samples will be drawn according to Section  $\underline{2}$ . This hypothesis-testing assay will be used by a specialised lab if a functioning assay is available in due time to ensure analysis and results ready for data base lock. If no functional assay is available the samples will be destroyed.

#### Antibodies (autoantibodies) & isotypes

The autoantibodies are used to confirm the clinical diagnosis of TD1M at screening and the assessments during the trial will give information of disease development. Further during the trial, isotypes of anti-insulin (IAA) and of anti-GAD autoantibodies will also be determined. Isotypes will change over time as the diabetes-associated immune response progresses or is modified by therapy. Therefore, autoantibody isotypes will provide information regarding the immune and disease status of an individual.

Autoantibodies will be drawn according to Section  $\underline{2}$ . The following autoantibodies will be analysed:

- Anti-GAD
- Anti-ZnT8
- Anti-IA2
- Anti-IAA, excepted at Visit 1

Additionally, isotypes for anti-IAA and -GAD will be evaluated, excepted at Visit 1.

Anti-IAA and –GAD isotypes will be analysed at a specialised laboratory and only if the sample is positive for anti-IAA or anti-GAD antibodies. These results will be reported to the investigator at the end of the trial.

